1.0 Objectives

1.1 Primary Objectives: To evaluate the objective response rate of low dose of inotuzumab ozogamicin as measured by the hematologic remission rate (CR + CR_p + CR_i) in patients in first, second or later salvage setting.

1.2 Secondary Objectives: To evaluate the overall safety profile and the efficacy; the efficacy is measured by the hematologic response rate (CR + CR_i + PR), durations of response (DoR) and remission (DoR1), progression free survival (PFS), and overall survival (OS)

2.0 Patient Eligibility

Inclusion Criteria:

1. Patients at least 12 years of age.
2. Patients with a diagnosis of CD22-positive ALL based on local immunophenotyping and histopathology) who have:
 - a. Refractory disease, defined as disease progression or no response while receiving their most recent prior anti-cancer therapy.
 - b. Relapsed disease, defined as response to their most recent prior anti-cancer therapy with subsequent relapse.
3. Performance status of 0 to 3.
4. Adequate renal function including serum creatinine $\leq 2 \times$ upper limit of normal (ULN) or estimated creatinine clearance ≥ 15 mL/min as calculated using the method standard for the institution.
5. Adequate liver function, including total serum bilirubin $\leq 1.5 \times$ ULN unless the patient has documented Gilbert syndrome, and aspartate and alanine aminotransferase (AST or ALT) $\leq 2.5 \times$ ULN. If organ function abnormalities are considered due to tumor, total serum bilirubin must be $\leq 2 \times$ ULN
6. No active or co-existing malignancy requiring chemotherapy or radiation within 6 months.
7. Female subjects of childbearing potential should be willing to use effective methods birth control or be surgically sterile, or abstain from heterosexual activity for the course of the study. Subjects of childbearing potential are those who have not been surgically sterilized or have not been free from menses for > 1 year. Effective methods of birth control include birth control pills or injections, intrauterine devices (IUDs), or double-barrier methods (for example, a condom in combination with spermicide).

8. Male subjects should agree to use an effective method of contraception starting with the first dose of study therapy through the duration of treatment.

Exclusion criteria:

1. Pregnant or nursing women
2. Known to be HIV+
3. Ph+ ALL
4. Active and uncontrolled disease/infection as judged by the treating physician
5. Unable or unwilling to sign the consent form
6. Prior allogeneic stem cell transplantation (ASCT) or other anti-CD22 immunotherapy within ≤4 months before first dose of study treatment.
7. Known CNS or extramedullary disease unless approved by the PI.
8. Monoclonal antibodies therapy within 2 weeks before study entry
9. Radiotherapy and cancer chemotherapy (except for intrathecal chemotherapy, hydroxyurea, and cytarabine. Cytarabine and hydroxyurea are allowed to be used emergently in case of leukocytosis) or any investigational drug within 2 weeks before study entry.
10. Evidence or history of veno-occlusive disease (VOD) or sinusoidal obstruction syndrome (SOS)

3.0 Treatment Plan

3.1 This is an open-label, single-arm, phase II clinical study.

3.2 All patients will be registered through CORe

3.3 Patients will receive inotuzumab ozogamicin at the dose of 0.8 mg/m² on Day 1 (+/- 3 days), and 0.5 mg/m² on Days 8 and 15 (+/- 3 days) of cycle 1. Subsequent cycles will consist of inotuzumab ozogamicin at the dose of 0.6 mg/m² on Day 1 (+/- 3 days) and 0.3 mg/m² on Day 8 (+/- 3 days). Patients will have a bone marrow aspiration performed on Day 14 and Day 21 (+/- 3 days). If marrow aspiration shows no disease, Cycle 2 could resume on Day 28 (+/- 7 days) at the dose level recommended in section 8.1.6. If persistence disease (defined by bone marrow blasts >5%), Cycle 2 would resume as early as Day 22 (+/- 7 days). Responding (CR, CRi, CRp) patients could receive up to 5 additional cycles. A maximum of 6 cycles will be administered.

3.4 In patients with an allogeneic donor, an allogeneic stem cell transplantation will be offered at any time after the first cycle of treatment with inotuzumab ozogamicin. Cycles are to be repeated every 3 to 4 weeks.

3.5 Responders will be permitted to receive up to five additional consolidation cycles of treatment with inotuzumab ozogamicin.

3.6 CSF prophylaxis consisting of an intrathecal regimen according to institutional guidelines during and after inotuzumab treatment will be left to the investigator's discretion.

3.7 Patients who relapse after achieving a response for at least 3 months can be retreated for up to 6 additional cycles.

4.0 Pretreatment evaluation

Procedure	Comments	Schedule
Informed Consent	Obtain standard informed consent approved by IRB	Within 21 days before therapy
Medical History	History of present illness, known allergies, prior cancer history as far as traceable including ALL regimens and drugs uses, and past medical/ surgical history as far as relevant.	Within 14 days of therapy
Physical Examination	Vital signs (temperature, heart rate, respiratory rate, blood pressure) and performance status.	Within 14 days of therapy
Concomitant Medications	Document concomitant medications in the medical record	Within 14 days of therapy
Hematology	CBC with differential and platelet count	Within 14 days of therapy
Biochemistry	at least creatinine, total bilirubin, uric acid, LDH, SGPT or SGOT	Within 14 days of therapy
Bone marrow	Aspirate and/or biopsy with flow cytometry for confirmation of diagnosis; a sample will be stored for PCR assessment	Within 21 days of therapy
Pregnancy test	Serum or urine, if female and child-bearing potential only	Within 14 days of therapy
Imaging studies	Chest X-ray and/or PET/CT as clinically indicated	Within 14 days of therapy

5.0 Evaluation During Study

Procedure	Comments	Schedule
Hematology	CBC with differential and platelet count	Weekly during cycles 1 to 6
Biochemistry	at least creatinine, total bilirubin, SGPT or SGOT	Cycle 1, prior to study drug infusion Cycle 2-6, prior to each study drug infusion and/or at the discretion of the treating physician.
Physical Examination	Focused physical examination	Prior to each treatment cycle
Bone marrow	Aspirate and/or biopsy (MRD) by flow multicolor cytometry and by polymerase chain reaction (PCR).	On day 14, 21 +/- 3 days of the first cycle, then every 2-3 cycles.

5.1 Follow-up

Patients will be followed up to 30 days after completion of treatment. Afterward they may be enrolled and followed for survival under protocol DR09-0223.

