7.0 Background

7.1 Salvage therapy in acute lymphoblastic leukemia (ALL).

Despite an exceptionally high rate of initial CR, many adults with ALL will relapse. Current strategies to induce a second remission translating into long-term survival are lacking. Cytotoxic chemotherapy results in modest CR rates of 30-40% in first salvage and 10-20% in later salvages. Few patients can be bridged to allo-SCT, 5-10% in some studies but as high as 30-40% in the German trials^{1,2}. This bridging to allo-SCT offers a chance of long term remissions and cures (<20-30%). One of the most exciting groups of compounds under investigation in relapsed refractory (R/R) ALL are monoclonal antibodies

targeting CD19 and CD22. Of these antibodies, blinatumomab and inotuzumab ozogamicin are in the most advanced investigational phases (Table 1).

Blinatumomab was granted FDA approval for the treatment of R/R ALL in December 2014. Furthermore, inotuzumab was found to be superior to best available therapy in a randomized trial in patients with R/R ALL and was granted FDA approval for the treatment of R/R B-cell precursor ALL in August 2017.

The randomized trial confirmed the findings of the initial phase II studies. Inotuzumab induces responses in 80% of the patients with a median survival of 7.7 months. The rate of VOD was 10%. The aim of this study is to reduce the rate of VOD without minimizing efficacy.

Table 1. Monoclonal antibodies in relapsed/refractory ALL

Parameter	N (%)			
	Blinatumomab		Inotuzumab	
	Pivotal Study, n=36	Confirmatory Study, n=189	Single dose n=49	Weekly n=40
Overall Response	25 (69)	81 (43)	28 (57)	24 (60)
Salvage Status				
Salvage 1	11 (31)	38 (20)	13 (27)	16 (40)
Salvage 2+	10 (28)	151 (80)	36 (73)	24 (60)
Median survival (months)	9.8	6.1	5.0	9.5

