7.4 Inotuzumab ozogamicin toxicity profile

Transient fever and hypotension were the 2 most frequent non-hematologic adverse events, and typically occurred shortly after the inotuzumab infusion. Liver function abnormalities were also observed, but tended to be reversible. Serious toxicity in the transplant group included the development of veno-occlusive disease (VOD) in five patients (23%). Four of the 5 patients had received multiple alkylating agents in the transplant preparative regimen, including clofarabine which may have predisposed them to VOD. Two of the 4 patients undergoing second ASCT developed VOD, suggesting this group of patients to be also at higher risk for VOD. In elderly ALL and in combination with low intensity chemotherapy, 4 patients (11%) developed a VOD, one of them post allogeneic stem cell transplantation. All but one patient had mild VOD that resolved subsequently. Only one patient developed a Grade 5 VOD after 2 cycles, was switched to miniHCV and ofatumumab, received 2 more additional courses, developed anasarca and multiple organ failure and expired thereafter. The safety profile of inotuzumab ozogamicin vs standard of care (SOC) was consistent with the initial studies. For inotuzumab vs SOC, Gr≥3 hepatobiliary AEs occurred in 9% vs 3% patients; any grade VOD occurred in 15 (14%) vs 1 (0.9%) patient (Gr≥3, 13 vs 1 patients). More patients proceeded to ASCT with inotuzumab (n=48) vs SOC (n=20); in the inotuzumab arm, 5 VOD cases (2 in patients with prior ASCT) occurred during treatment and 10 after subsequent SCT (2 fatal).

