8.3 Recommendations to reduce the risk of VOD for patients proceeding to ASCT

- For patients planning to receive an allogeneic ASCT, it is recommended that treatment with inotuzumab ozogamicin be limited to 2 cycles of induction or the fewest number of cycles required to achieve a CR/CRi/CRp (if CR/CRi/CRp not achieved after 2 cycles).
- The risk of relapse must be balanced against the potential risk of toxicity associated with beginning ASCT soon after the last dose of inotuzumab ozogamicin; however, approximately 5-6 weeks between inotuzumab and ASCT may be reasonable for most patients.
- Healthcare providers should use their clinical judgment to determine the most appropriate course of therapy for prophylactic treatment before the start of conditioning therapy according to standard of care (eg, prophylactic ursodeoxycholic acid at 12-15 mg/kg/day, beginning 2 weeks before the start of conditioning therapy).
- Use the least hepatotoxic conditioning regimen and, specifically, avoid using regimens that contain 2 alkylating agents and or that combine an alkylating agent with higher dose TBI (defined as >12 Gy).
- If using a busulfan-containing conditioning regimen, please consider using pharmacokinetically-dosed busulfan.
- When possible, avoid the concomitant use of hepatotoxic drugs peri-transplant.
- If significant liver toxicity occurs, consult a gastroenterology and/or hepatology service.
- When evaluating liver toxicity, inform the radiologist of the potential for hepatic vascular disease. When VOD is in the differential diagnosis, a right upper quadrant ultrasound with colorflow doppler (including resistive indices to hepatic artery flow and evaluation of hepatic venous outflow) should be performed. In addition, the radiology report should describe the degree of gall bladder wall thickening in millimeters and the volume of ascites should be estimated as closely as possible (i.e., small and localized, moderate and generalized, or large and generalized).
- Defibrotide may be used in the setting of severe VOD
- If a patient will proceed to ASCT under the care of different physicians, these recommendation should be reviewed with the new treating physicians.

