12.0 Reporting Requirements

Adverse event reporting and recording will be as per the NCI criteria and the MDACC Leukemia Specific Adverse Event Recording and Reporting Guidelines. All subjects will be monitored for AEs during the study. AEs will be recorded from the first dose through 30 days after the last dose. Serious Adverse Events (SAEs) will be captured starting from the date of consent. Any serious adverse events that occur after the 30 day time period that are related to the study treatment will also be reported.

The descriptions and grading scales found in the revised NCI Common Terminology Criteria for Adverse Events (CTCAE) version 4.03 will be utilized for adverse event reporting. (<http://ctep.cancer.gov/reporting/ctc.html>).

The Principal Investigator will sign and date the Adverse Event Record (AE log) for each patient at the completion of each course. Following signature, the AE logs will be used as source documentation for the adverse events for attribution.

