- **All life-threatening or fatal events**, that are unexpected, and related to the study drug, must have a written report submitted within **24 hours** (next working day) of knowledge of the event to the Safety Project Manager in the IND Office.
- Unless otherwise noted, the electronic SAE application (eSAE) will be utilized for safety reporting to the IND Office and MDACC IRB.
- Serious adverse events will be captured from the time of the first protocol-specific intervention, until 30 days after the last dose of drug, unless the participant withdraws consent. Serious adverse events must be followed until clinical recovery is complete and laboratory tests have returned to baseline, progression of the event has stabilized, or there has been acceptable resolution of the event.
- Additionally, any serious adverse events that occur after the 30 day time period that are related to the study treatment must be reported to the IND Office. This may include the development of a secondary malignancy.

Reporting to FDA:

- Serious adverse events will be forwarded to FDA by the IND Sponsor (Safety Project Manager IND Office) according to 21 CFR 312.32.

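### Scheduled follow-up and AE recording end at day 30, before a transplant at the suggested interval, so the VOD rate and the VOD stopping rule may run low

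*Combined protocol and SAP*

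**What the plan says.** Section 5.1 sets the end of scheduled observation: "Patients will be followed up to 30 days after completion of treatment. Afterward they may be enrolled and followed for survival under protocol DR09-0223". Section 12.0 sets the matching limit for safety data: "AEs will be recorded from the first dose through 30 days after the last dose". After that, sections 12.0 and 12.1 leave one route open, with no end date: "any serious adverse events that occur after the 30 day time period that are related to the study treatment must be reported". SAE reporting to the drug supplier ends at 28 days (section 12.2).

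VOD is central to the study. Section 7.1 says: "The aim of this study is to reduce the rate of VOD without minimizing efficacy". In section 11.0 it is the only event in the toxicity stopping rule, counted at any grade if judged related to inotuzumab. No observation window is given.

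Transplant is a path the protocol itself provides. Under section 3.4, for patients with a donor, "an allogeneic stem cell transplantation will be offered at any time after the first cycle of treatment". On timing, section 8.3 says "approximately 5-6 weeks between inotuzumab and ASCT may be reasonable for most patients". It also foresees a change of care team: "If a patient will proceed to ASCT under the care of different physicians, these recommendation should be reviewed with the new treating physicians". That hands over advice on lowering VOD risk. It does not ask the new team to report VOD back to the study.

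**The concern.** A patient transplanted at the suggested interval leaves scheduled observation before the transplant takes place, and the protocol's own background places much of the VOD after transplant. A late VOD is not lost by rule, but it has to be noticed without a scheduled contact, judged serious and judged related.

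Two results are exposed. The reported VOD rate could be too low, and a low rate is what the study hopes to see with the reduced dose. The stopping rule could also trigger less often than Table 4 indicates, because Table 4 holds only if every countable VOD is counted.

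**Working it through.** **Timing.** 5-6 weeks is 35-42 days, which is 5 to 12 days beyond the 30-day limit.

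**Share of VOD after transplant.** For the inotuzumab arm of the randomized trial, section 7.4 gives "5 VOD cases (2 in patients with prior ASCT) occurred during treatment and 10 after subsequent SCT (2 fatal"). That is 10/15 = 67%, with a Clopper-Pearson 95% interval of 38% to 88%. In the elderly combination study in the same section it is 1 of 4. Neither source gives the share arising after day 30.

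**Reproducing Tables 3 and 4.** The inputs from section 11.0 are a Beta(0.4, 1.6) prior, a limit of 0.20, a cut-off of 0.92, looks at 8, 16, 24, 32 and 40 patients, and a maximum of 48.

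- Boundary at n: the smallest x with Pr(p > 0.20 | Beta(0.4 + x, 1.6 + n - x)) > 0.92. This gives 4/8, 6/16, 8/24, 11/32 and 12/40, as in Table 3.
- Exact binomial recursion over the looks gives early-stopping probability (mean patients treated) of 0.174 (43.0) at a true rate of 0.20, 0.652 (29.8) at 0.30 and 0.949 (17.8) at 0.40. Table 4 has 0.17 (43.0), 0.65 (29.8) and 0.95 (17.8).

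The plan's own figures are correct if capture is complete.

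**Incomplete capture.** Let c be the share of related VOD that reaches the monitoring data. The rule then behaves as if the true rate were (true rate) x c. The value of c is an assumption:

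- 13/15: every Grade 3 or higher case is reported as a related SAE and lower grades are missed (section 7.4: 13 of 15 were Grade 3 or higher).
- 3/4: every post-transplant case is missed, at the 1-of-4 split.
- 2/3: an intermediate value, with no source in the documents.
- 1/3: every post-transplant case is missed, at the 10-of-15 split (5/15). This is the worst case.

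| c | Rate seen if true rate is 30% | P(stop) | Mean patients | Rate seen if true rate is 14% |
|---|---|---|---|---|
| 1 | 30% | 0.65 | 29.8 | 14% |
| 13/15 | 26% | 0.45 | 35.7 | 12.1% |
| 3/4 | 22.5% | 0.28 | 40.3 | 10.5% |
| 2/3 | 20% | 0.17 | 43.0 | 9.3% |
| 1/3 | 10% | 0.008 | 47.7 | 4.7% |

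**A fixed shortfall instead of a fraction.** 15 cases at 14% imply about 15/0.14 = 107 patients. If 10/107 = 9.3% of patients have a missed post-transplant VOD, a true 30% is seen as 20.7%. The chance of stopping is then 0.20, with 42.4 patients on average.

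**At rates nearer those in the background.** At a true 14%, the chance of stopping is 0.037 with full capture and 0.019 at 13/15. At a true 10% it is 0.008 and 0.004.

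**The case against.** The strongest reply is that late VOD is already covered. Related SAEs must be reported after day 30 without an end date, section 12.1 defines serious broadly, and 13 of 15 cited cases were Grade 3 or higher. Few related post-transplant cases should fail that test. For the stopping rule, relatedness is no extra hurdle either, because the rule already requires it. All of this stands. For Table 3 the added losses are non-serious cases and cases nobody is scheduled to look for; relatedness is an added filter only for an all-VOD rate. It makes c = 1/3 improbable, since that value would require every post-transplant case to go unreported.

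The range of c is also open to attack. The 3/4 comes from a different population. The 10 of 15 is a share after transplant, not after day 30. The 5-6 weeks is a recommendation, and transplant uptake in this trial is unknown. The 13/15 itself assumes that both lower-grade cases arose late and were not serious. These points limit what can be said about size.

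Further, 30% is well above the whole-population rates in the documents (10% in section 7.1; 14% and 11% in section 7.4), and at 10-14% the rule seldom stops whatever the capture. That is right, but a safety rule is needed for the case where the true rate is high.

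Lastly, the VOD rate is not a listed objective, a single-arm trial cannot attribute a low rate to dose, and section 7.4 links some post-transplant VOD to conditioning. These are reasons to report post-transplant VOD separately. They are not reasons to leave its collection unscheduled when section 7.1 makes VOD the study's aim.

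**Conclusion.** The concern holds. Scheduled observation ends before a transplant at the suggested interval, and the later reporting route is narrower than the event the stopping rule is meant to count. The direction of any bias is downward. Its size is not determined by the documents.

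If serious-event reporting works fully, the loss is at most about 2/15 = 13% of cases on the cited severity split. Even that lowers the chance of stopping at a true 30% rate from 0.65 to 0.45. With weaker reporting it could fall much further, to 0.008 at the extreme. At true rates of 10-14% the effect on stopping is small, and the main harm is to the reported VOD rate: a true 14% seen as 12.1% to 4.7% could be mistaken for a benefit of the lower dose.

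The boundaries in Table 3 are not wrong. What is at risk is the completeness of the counts put into them. This should be fixed; confidence in its practical size is medium, because c is assumed.

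**What to change.** - **Sections 5.1 and 12.0:** require active collection of VOD of any grade for every treated patient, by chart review or contact with the transplant team, through a stated fixed window that covers the period after any subsequent transplant. Record attribution, but do not make it a condition of capture.
- **Section 8.3:** where care passes to other physicians, ask them to report VOD back to the study.
- **Section 11.0:** state that related VOD in this window counts toward Table 3 and the reported rate. Keep the looks at every 8 patients, update the count as late cases arrive (the section already applies the rule throughout the trial), and show at each look how many patients are still inside the window.
- **Reporting:** give on-treatment and post-transplant VOD separately, and all VOD beside related VOD.

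The 20% limit, the prior and Table 4 need re-checking only if the rule is changed to count VOD regardless of attribution.

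The cost is a protocol amendment and some data collection after transplant, with no new procedure, no extra patients and no delay to the looks. The observed VOD rate may look less favourable. Early looks will still include patients with incomplete follow-up, so the change reduces the gap from Table 4 at those looks but does not remove it.

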6.0 Criteria for Response

Complete remission (CR):

Normalization of the peripheral blood and bone marrow with 5% or less blasts with a granulocyte count of $1 \times 10^9/L$ or above and a platelet count of $100 \times 10^9/L$ or above and absence of extramedullary disease.

Complete remission without platelet recovery (CRp):

As above except platelets $< 100 \times 10^9/L$

Complete remission with incomplete count recovery (CRI):

CR without recovery of neutrophils or platelet counts

Partial response (PR):

As above, except for the presence of 6-25% marrow blasts.

MRD negativity:

MRD levels will be continuously assessed during induction and consolidation therapy by 6-color multiparameter flow. MRD negativity will be defined by a value of no more than 10^{-4} and confirmed on a second bone marrow aspiration/biopsy performed after a subsequent cycle.

No response (NR):

Patients will be considered non-responders if no response is achieved after 2 cycles.

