8.1.5 Dose delays

If patients do not meet the criteria below on the day of the scheduled treatment, the administration of the dose will be delayed.

1. No evidence of progressive disease or relapse prior to the start of each cycle; however, treatment may continue, at the judgment of the investigator, in patients with only extramedullary CNS and/or testis relapse.
2. Prior to the start of each cycle, decrease in blast percentage or stable disease (ie, not more than a 50% increase in blast percentage) based on the most recent bone marrow evaluation.
3. Recovery to grade 1 or baseline non-hematologic clinically significant test article-related toxicity (including liver function test abnormalities, not including alopecia).

4. Serum bilirubin $\leq 1.5 \times$ ULN, and AST or ALT $\leq 2.5 \times$ ULN (or if elevated due to tumor, bilirubin $\leq 2 \times$ ULN). Isolated AST or alkaline phosphatase elevations need not result in dose delays if not related to hepatobiliary organs (eg, alkaline phosphatase elevations due to bone involvement). Inotuzumab ozogamicin dosing should be permanently discontinued for any patients with possible, probable or confirmed VOD or other severe liver toxicity.
5. Any serum creatinine level associated with a measured or calculated creatinine clearance ≥ 15 mL/min using the method standard for the institution.
6. Prior to the start of each cycle, for subjects with pre-treatment ANC $\geq 1 \times 10^9/L$: ANC $\geq 1 \times 10^9/L$.
7. Prior to the start of each cycle, for subjects with pre-treatment platelets $\geq 50 \times 10^9/L$: platelets $\geq 50 \times 10^9/L$.
8. Subjects with pre-treatment ANC $< 1 \times 10^9/L$ and/or platelets $< 50 \times 10^9/L$: ANC and platelets must recover to baseline values obtained for the prior cycle, or ANC $\geq 1 \times 10^9/L$ and platelets $\geq 50 \times 10^9/L$, or the most recent bone marrow must demonstrate stable or improved disease, and the ANC and platelets are believed to be low due to disease.

There are no ANC or platelet count requirements for Cycle 1 day 1, as dosing criteria are relative to pre-treatment values. While doses given within a treatment cycle (ie, day 8) need not be delayed due to neutropenia or thrombocytopenia, dose delays within a cycle are recommended for non-hematologic toxicity.

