The hematologic remission rate will be estimated along with the 95% credible interval. Data from all subjects who receive any study drug will be included in the safety analyses. Subjects who entered the study but did not take any of the study drug and had this confirmed will not be evaluated for safety. The severity of the toxicities will be graded according to the NCI CTCAE v4.03 whenever possible. We will follow standard reporting guidelines for adverse events. Safety data will be summarized by AE category, severity and frequency. The proportion of patients with AEs will be estimated, along with the Bayesian 95% credible interval. Kaplan-Meier method will be used to assess the overall survival (OS), progression-free survival (PFS), duration of response (DoR) and durations of remission (DoR1). The rate of hematologic response (CR + CRI + PR) will also be estimated.

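### Partial response requires no fall in marrow blasts from baseline, so a patient with low blasts at entry can count as a secondary-endpoint responder without improving

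*Combined protocol and SAP*

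**What the plan says.** Section 6.0 describes complete remission (CR) as "Normalization of the peripheral blood and bone marrow with 5% or less blasts with a granulocyte count of" a stated level, plus a platelet threshold and no extramedullary disease. CRp and CRi follow as relaxations of the count requirements. PR comes next: "As above, except for the presence of 6-25% marrow blasts". The text does not say whether *as above* points to CR, CRp or CRi. Section 6.0 has no stable-disease or progressive-disease category. On non-response it says "Patients will be considered non-responders if no response is achieved after 2 cycles".

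Section 2.0 admits refractory or relapsed disease without a blast threshold. The second route is "Relapsed disease, defined as response to their most recent prior anti-cancer therapy with subsequent relapse".

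Two other sections classify marrow blasts:

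- Section 3.3, on the timing of cycle 2: "If persistence disease (defined by bone marrow blasts >5%), Cycle 2 would resume as early as Day 22".
- Section 8.1.5 item 2, on what must be true before each cycle: "decrease in blast percentage or stable disease (ie, not more than a 50% increase in blast percentage". The consequence of failing is "If patients do not meet the criteria below on the day of the scheduled treatment, the administration of the dose will be delayed".

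PR enters one planned analysis by name, in section 11.0: "The rate of hematologic response (CR + CRI + PR) will also be estimated". Sections 1.2 and 11.0 list DoR separately from duration of remission (DoR1), but neither says which responses start the DoR clock. The primary endpoint in section 11.0 is CR + CRp + CRi.

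**The concern.** A response category should record a change brought about by treatment. This one records a state. For a patient who starts above 25% blasts the two coincide, because reaching the band means blasts have fallen. For a patient who starts at 25% or below they do not. If blood, counts (where required) and extramedullary status also qualify, that patient can satisfy PR before the first dose and keep satisfying it with no change.

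Three things are at stake:

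- The secondary hematologic response rate can include patients who did not respond, so it is biased upward.
- If DoR includes PR, those patients contribute a duration that starts without a response.
- The no-response label after two cycles depends on what counts as a response, and section 10.1 uses that label. A patient with an unchanged marrow could be PR in one place and read as a non-responder in another.

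Under 8.1.5 the same marrow may also be beyond stable disease, so the plan can classify one result in two incompatible ways.

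**Working it through.** **Inputs.** PR band 6-25% (section 6.0); no minimum blasts at entry (2.0); stable disease is a rise of at most 50% (8.1.5 item 2); full enrolment 48, first stage 18 (11.0). The documents give no figure for PR in this trial, so there is none to reproduce.

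**Is the primary design involved?** Exact two-stage binomial sums for the section 11.0 rule (stop at 6 or fewer of 18, succeed at 21 or more of 48, 35% versus 50%) give:

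| Quantity | Stated | Recomputed |
|---|---|---|
| Type I error | 0.113 | 0.1127 |
| Power | 78.3% | 78.5% |
| Early termination at 35% | 0.549 | 0.549 |
| Expected sample size at 35% | 31.5 | 31.5 |

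PR is not among the counted outcomes, so changing its definition alters none of these.

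**Blast change.** For baseline x and follow-up y, relative change = (y − x)/x. PR needs 6 ≤ y ≤ 25 plus the *as above* conditions, which are taken as met here.

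| x → y | Relative change | 6.0 | 8.1.5 item 2 |
|---|---|---|---|
| 15% → 15% | 0% | PR | stable |
| 8% → 12% | +50% | PR | stable (at the limit) |
| 8% → 13% | +62.5% | PR | beyond stable |
| 10% → 25% | +150% | PR | beyond stable |
| 16% → 25% | +56% | PR | beyond stable |
| 17% → 25% | +47% | PR | stable |

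**Where the conflict with 8.1.5 begins.** The largest PR value is 25%. It breaches the limit when 25 > 1.5x, that is x < 25/1.5 = 16.7%. This gives three zones:

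- Baseline above 25%: PR always means a fall.
- Baseline from 16.7% to 25%: an unchanged or rising marrow can be PR, but it stays within stable disease under 8.1.5.
- Baseline below 16.7%: a marrow can be PR under 6.0 and beyond stable disease under 8.1.5.

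This assumes that the 50% is a relative change and that the comparator is the pretreatment marrow. If the 50% meant percentage points, no value in the PR band could breach it. Item 2 relies on the most recent marrow and does not name its comparator.

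**Size.** Each PR without a fall adds 1/48 = 2.1 percentage points to the secondary rate, if all 48 patients form the denominator. If the trial ended at 18, each would add 1/18 = 5.6 points. The number of such patients cannot be derived. Over an assumed range of 1 to 5 of 48, the addition runs from 2.1 to 10.4 points (5/48); that range is illustrative only.

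**The case against.** The strongest reply is that the PR line is narrower than it looks and little depends on it. Most of that is fair.

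- **PR is not the blast band alone.** A reader might infer that any 6-25% marrow scores PR. The *as above* wording carries over at least blood normalization and no extramedullary disease, and count recovery too if it refers to CR. Referring to CR is plausible, since only the CR text contains the blast limit that PR replaces. This reduces the number of patients affected, but a low-burden patient with adequate counts still qualifies.
- **8.1.5 is not a response definition.** A reader might infer a direct contradiction. The 50% limit is a check before redosing, and missing it delays a dose. The unchanged 15% marrow conflicts with nothing there. What remains is inconsistent classification when baseline is below 16.7%, on the reading stated above.
- **PR does not clearly shield a progressing patient from removal.** Section 10.1 lists progressive disease separately from no response, section 10.8 adds the investigator's judgement of benefit, and section 3.3 treats only CR, CRi and CRp as responding. This stands, although 6.0 does not define progressive disease.
- **Frequency may be low.** Table 2 in section 7.3.1 shows 0 PRs in 89 earlier patients. The one-sided 95% upper bound is 1 − 0.05^(1/89) = 3.3%, or about 1.6 of 48. The PR definition used in those studies is not shown, so this is only indicative, but it gives no support for a figure as high as five.
- **The DoR effect is inferred.** Listing DoR apart from DoR1 suggests that DoR includes PR, but the plan does not say so.
- **No decision rule uses the affected rate.** It is estimated only. This limits the priority of the point but does not make the rate correct.

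**Conclusion.** The point holds in limited form. As written, PR can be assigned to a patient whose marrow blasts are unchanged or higher, provided baseline is 25% or less and the *as above* conditions are met. The bias in the secondary hematologic response rate is upward, at 2.1 percentage points per such patient in 48. The total is unknown because the documents give no baseline blast distribution. The inconsistency with 8.1.5 is confined to baselines below 16.7% and rests on reading the 50% as relative to the pretreatment marrow. The effect on DoR is conditional on DoR including PR.

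A reader might go further and infer that the primary result is inflated or that the secondary rate is overstated by about ten points. The documents support neither. PR is outside CR + CRp + CRi, so both Simon stages and the sample size stand, and no figure in the plan fixes the number of affected patients. This is a definition to correct before analysis, not a flaw in the trial's main test.

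**What to change.** In section 6.0, keep the existing PR conditions and make three changes:

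1. Say which category *as above* refers to.
2. Add that, for the secondary response rate and DoR, PR also requires a prespecified relative decrease in marrow blasts from the pretreatment marrow. At least 50% is one example; the documents give no threshold, so the sponsor should choose and justify it. A 6-25% marrow without that fall is then not counted as a response in these two analyses.
3. State which responses start the DoR clock.

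Separately, reconcile the PR, no-response and progressive-disease wording in 6.0 and 10.1 with the stable-disease limit in 8.1.5, including the comparator for that limit. How those sections should govern treatment is for the sponsor and investigator; no stopping rule is proposed here.

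The cost is a few sentences. Section 4.0 already requires a pretreatment marrow, so no procedure is added, but its blast percentage must be recorded for every patient. The secondary response rate may be slightly less favourable. The primary analysis and sample size do not change.
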